Title: **Symptoms of Polycystic Ovarian Syndrome Ameliorated by Responses of Keto-Adaptation**
Short title: **SPARK**

PI:
[name], CSCS
Research Scientist, Department of Human Sciences
The Ohio State University
[name]
[name]
Office: [contact] | [contact]

Co-PI/External Collaborator:
[name], MS, RD, LD, Co-I
Senior Research Dietician
The Ohio State University
[name]
[name]
Office: [contact] | [contact]

[name], RD
Professor, Department of Human Sciences
The Ohio State University
[name]
[name]
Office: [contact] | [contact]

[name]
Physician, Obstetrics and Gynecology
The Ohio State University Wexner Medical Center
[name]
[name]
Office: [contact] | [contact]

ABBREVIATIONS

BHB	Beta hydroxybutyrate
KD	Ketogenic Diet
FSH	Follicle Stimulating Hormone
LBM	Lean body mass
LH	Luteinizing hormone
PCOS	Polycystic Ovarian Syndrome
DEXA	Dual-Energy X-ray Absorptiometry
mL	milliliters
mg	Milligrams
h	Hour
ANOVA	Analysis of variance
AE	Adverse event
USG	Urine Specific Gravity
yr	Year

STUDY SYNOPSIS

Study Title	Symptoms of PCOS Ameliorated by Responses to Keto-adaptation
Short Title	SPARK
Study Design	A 12-week randomized, 2 arm intervention testing responses to ketogenic diet intervention vs mixed diet with exogenous ketone supplement in women diagnosed with PCOS.
Study Participants	
• Women diagnosed with PCOS between ages 18-40
Planned Study Period	August 2024-August 2025
OUTCOMES	
Primary	Changes in anovulatory status in women with PCOS
Secondary	
• Changes in reproductive hormones such as progesterone, estrogen, LH, FSH• Analysis of potential predictive metabolic baseline characteristics• Differences in blood metabolites (metabolic and lipids).
Exploratory	
• Examine cardiovascular function and ovarian morphology using magnetic resonance imaging (MRI).

SUMMARY AND BACKGROUND

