As the hormone dynamics could shift when an individual is on a ketogenic intervention, testing will be moved to biweekly to capture these changes. These changes are already in effect in the SPARK001 participant in the study.

IMPACT

Our intent is to produce preliminary feasibility and efficacy data to inform the design of a future fully-powered, clinical trial that will examine whether ketogenic dietary intervention strategies are effective in ameliorating multiple adverse signs and symptoms in women with an incurable endocrinopathy. Thus, providing evidence suggesting this approach as a safe and effective treatment intervention in women diagnosed with PCOS.

OUTCOMES

Primary

Changes in anovulatory status in women with PCOS

Secondary

- Changes in reproductive hormones such as progesterone, estrogen, LH, FSH
- Analysis of potential predictive metabolic baseline characteristics
- Differences in blood metabolites (metabolic and lipids).

Exploratory

- Examine cardiovascular function using magnetic resonance imaging (MRI)
- Examine ovarian morphology through MRI.

PARTICIPANTS

This study aims to recruit 40 female participants between the ages of 18 to 40yr who have been diagnosed with PCOS. Each participant must meet all the inclusion criteria and none of the exclusion criteria at screening in order to participate.

Inclusion criteria:

- Female
- Ages 18 – 40 years
- Participant is willing and able to comply with all study procedures including the following prior to Test Day: fasting (>10 h; water only), no alcohol (>24 h), no exercise (>24 h), no acute illness and controlled feeding before the Test Day, maintain diet, exercise, medication, and supplement habits throughout the study.
- Participants with PCOS symptoms including oligomenorrhea-anovulation or spontaneous intermenstrual periods.
- BMI >18kg/m
- Participant understands the study procedures and signs forms providing informed consent to participate in the study.
- **Must have access to smart phone, computer or tablet to access diet.**

Exclusion criteria:

- Participant follows a low-carbohydrate diet (<30% energy from carbohydrate)
- Participant has non-PCOS etiologies of anovulation, menopause or the removal of the ovaries.
- Participant has history of type 1 diabetes
- Participant has loss of 10% bodyweight in the last 6 months
- Participant is pregnant or breast feeding
- Participant has a condition the Investigator believes would interfere with his ability to provide informed consent.

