[figure not shown]
Sample Size. In our pilot trial with a sample size of 20 participants in each intervention, we acknowledge the limitations in statistical power due to the small sample. However, for this pilot trial we plan to recruit 40 participants to investigate the effects on ovulation. The results of this pilot trial will provide initial insights, but it is essential to acknowledge the limitations imposed by the small sample size.

Recruitment:

Recruitment will occur through well-established methods at OSU which include word of mouth, ResearchMatch database, social media engagement and flyers.

METHODS

SPARK-Pilot Study Design

Study overview:

Figure 2 | Study schematic, showing timeline for a study day.

Study Procedures

Study Day	Screening	Test Day	Daily
Visit to Study Center	X	X	
Informed consent	X		
Medical intake questionnaire, diet assessment, anthropometrics ¹	X		
Body Composition Scan ²		X	
Basal Body Temperature ³			X
Urine based Ovulation predication test ⁴			X
Fingerstick Measurements ⁵			X
Hydration Status ⁶		X	
Whole blood collection ⁷		X	
Surveys ⁸		X	
Cardiovascular and Ovarian MRI ⁹		X	

1. Medical intake questionnaire and diet assessment questionnaire are attached in **Appendix**. Anthropometric data will include: Hip and Waist circumference, BMI, height and weight.
2. Lean Body Mass and fat mass assessments will be done by DXA measurement at weeks 0 and 8.
3. Participants will also be provided with an intravaginally inserted OvuCore Sensor that is designed for measuring core body temperature which rises as progesterone is

releases. Participants will insert these monitors before sleep and wear them throughout the night

4. Participants will be provided with urine ovulation predictor kit testing strips to use during the duration of the study as a tertiary predictor of potential ovulation
5. Daily fasting glucose/ketones will be assessed using capillary finger stick lancing. A small drop of blood (i.e., the size of a grain of rice) will be obtained once daily, while fasting, using enzymatic strips fitted for a handheld analyzer (KetoMojo). All the data will be stored in the device's internal memory until retrieved by the study team during test visits.
6. Prior to blood collection, participants will be asked to completely void their bladder. And hydration status will be determined via urine specific gravity (USG) reporting <1.025 . Urine will be tested for pregnancy status.

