made meal services (Pangea Keto, Factor, Fresh and Lean). After the initial 2 weeks, and until completion of the 8-week intervention, the participants will not be supplied with all their food but will continue to receive educational materials, recipe guides and dietitian consultation as needed. Participants will have 24-hour access to the dietetic team to answer questions. After the initial 2 weeks, participants will switch to a self-guided dietary approach. Adherence will be prospectively evaluated throughout the study period. Subjects will be asked to use the meter each morning and to submit the results to the research team through a secure KetoMojo provider/consumer sharing application. Results will be recorded by a member of the research team. Levels of ketosis and glucose will be monitored daily. Participants will be asked to maintain levels of ketones that are equal or greater than 0.5mmol/L.

DATA ANALYSIS AND STATISTICAL METHODS

Statistical Plan: To evaluate the impact of the ketogenic diet intervention on menstrual cycle regularity in women with PCOS, we have the following data analysis plan:

- 1) Descriptive Analysis: We will provide concise summaries of menstrual cycle attributes such as cycle length, variability, and ovulation status for participants at baseline.
- 2) Menstrual Cycle Regularity Assessment: Survival analysis techniques, including Kaplan-Meier curves and log-rank tests, will be employed to compare the timeframe required to establish regular menstrual cycles (21-35 days range). Observations censored due to drop-outs or non-occurrences of events will be appropriately handled.
- 3) Ovulation Pattern Analysis: We will utilize logistic regression analysis to assess the effect of the ketogenic diet on the incidence of ovulation in PCOS women, considering each cycle as an independent statistical unit. This analysis will offer quantifiable insights into the probability of ovulation in the study population, considering potential confounders like age, BMI, and initial menstrual cycle characteristics.
- 4) Effect Size Estimation: Hazard ratios and their confidence intervals will be calculated to quantify the influence of the ketogenic diet on attaining regular menstrual cycles.

5) Significance Testing: The proportion of participants achieving regular menstrual cycles in each diet group will be compared using appropriate statistical tests such as the chi-square test.

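### The only between-arm analysis of ovulation counts menstrual cycles, not women, so its denominator depends on cycling after randomisation and can omit women who have no completed cycle

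*Protocol*

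**What the plan says.** The Study Synopsis and the Outcomes section give the primary outcome as "Changes in anovulatory status in women with PCOS", which is a state of a woman.

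Under Data Analysis and Statistical Methods, item 3 is a logistic regression whose stated purpose is: "assess the effect of the ketogenic diet on the incidence of ovulation in PCOS women, considering each cycle as an independent statistical unit". Possible confounders named there are age, BMI and initial cycle characteristics. The other items do not compare ovulation between arms:

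- Item 1 is a baseline description.
- Items 2 and 4 concern time to regular cycles (log-rank test, hazard ratios). The remark on censoring when the event does not occur belongs to item 2.
- Item 5 compares the proportion of participants who reach regular cycles.

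Entry is open to "Participants with PCOS symptoms including oligomenorrhea-anovulation or spontaneous intermenstrual periods". The planned size is a "sample size of 20 participants in each intervention". The synopsis describes "A 12-week randomized, 2 arm intervention testing responses to ketogenic diet intervention", while the Diet Intervention section gives the intervention as eight weeks. The protocol does not say what counts as a cycle in item 3, or how a woman with no cycle, or only an unfinished one, enters the model.

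**The concern.** When cycles are the rows of the model, the denominator is the number of cycles observed after randomisation. Item 2 tests whether the diet changes cycling, so the plan itself treats cycling as a possible effect of treatment. The denominator of item 3 is therefore partly an outcome.

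Two consequences follow if only completed cycles are rows. A woman who stays amenorrhoeic, or whose cycle is too long to finish in the window, is absent from the model although she has plainly not ovulated regularly. A woman who moves from no bleeding to anovulatory bleeding adds failures to her arm. An arm that restores bleeding can thus look worse per cycle while doing better per woman.

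This is a different fault from treating one woman's repeated cycles as independent. GEE or a random effect deals with correlation among rows that exist; it cannot restore women who have none. Adjustment for baseline covariates cannot restore them either.

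**Working it through.** The protocol gives no ovulation rate, effect size or cycle-length distribution, so there is no figure to reproduce. The inputs from the protocol are 20 women per arm and a window of 12 weeks (84 days) or 8 weeks (56 days). Everything else below is assumed for illustration.

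**1. Per woman against per cycle (assumed counts).**

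| | Ketogenic | Mixed diet + ketone ester |
|---|---|---|
| Ovulate in 2 cycles each | 8 women | 4 women |
| One anovulatory cycle | 8 women | 2 women |
| No bleed | 4 women | 14 women |
| Women ovulating | 8/20 = 40% | 4/20 = 20% |
| Ovulatory cycles, completed cycles only | 16/(16+8) = 67% | 8/(8+2) = 80% |
| The same, each non-bleeding woman scored as one anovulatory unit | 16/(24+4) = 57% | 8/(10+14) = 33% |

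The order reverses when non-bleeding women have no row and returns when each supplies one. The result hinges on a rule that the protocol does not state.

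**2. A second scenario.** Let a share q of women have no cycle under control. Women who cycle ovulate with probability p = 0.5. The ketogenic diet restores cycles in half of the non-cyclers, and restored women ovulate with probability r. Each contributing woman supplies one unit.

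- All randomised women: control (1−q)p; ketogenic (1−q)p + (q/2)r. The difference is (q/2)r, which is always positive.
- Contributors only: control p; ketogenic [(1−q)p + (q/2)r]/[(1−q) + q/2]. The difference is (q/2)(r−p)/(1−q/2), which takes the sign of r−p.

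With q = 0.4 and r = 0.2, all women give 0.34 − 0.30 = +4.0 points. Contributors give 0.34/0.80 − 0.50 = 0.425 − 0.50 = −7.5 points. For q from 0.2 to 0.5 and r from 0.2 to 0.5, the difference runs from +2.0 to +12.5 points in all women and from 0 to −10.0 points among contributors. If r exceeded p, the contributor difference would be positive, so the direction is not determined.

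**3. How many women might have no completed cycle.** For a steady cycle length L and a random starting phase, the chance of one bleed-to-bleed cycle in W days is (W−L)/L when L ≤ W < 2L, and 0 when W < L.

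- L = 45: (84−45)/45 = 87% in 84 days; (56−45)/45 = 24% in 56 days.
- L = 60: (84−60)/60 = 40% in 84 days; 0% in 56 days.

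A simulation let usual cycle length vary between women (lognormal, log-SD 0.4), with a random phase at day 0 and variation in the next cycle (log-SD 0.15). Share of women with no completed cycle:

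| Median usual length (days) | 35 | 45 | 60 | 90 |
|---|---|---|---|---|
| 84 days, bleed to bleed | 15% | 31% | 55% | 84% |
| 84 days, cycle starts at day 0 | 1% | 6% | 20% | 57% |
| 56 days, bleed to bleed | 43% | 65% | 84% | 97% |
| 56 days, cycle starts at day 0 | 12% | 29% | 57% | 88% |

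The loss depends heavily on the definition of a cycle and on which duration applies.

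**The case against.** The strongest reply is that item 3 says only that cycles are the unit. It does not require a cycle to be completed or bounded by two bleeds. Temperature tracking is nightly, so an interval that never closes could be scored as one anovulatory unit, and an SAP that is not shown may say so. This stands: the loss of women is conditional, and its size falls sharply under a looser definition. It does not dispose of the point. Even then the number of units per woman would depend on cycling after randomisation, and the choice of the cycle as unit is made in the protocol itself.

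A reader might infer that the most severely affected women certainly leave the primary comparison, or that the trial will reach the wrong direction. The documents support neither. No analysis is labelled primary; item 3 takes that place only because nothing else compares ovulation. The reversal in the first illustration needs 14 of 20 non-bleeding women in one arm against 4 of 20 in the other, a contrast found nowhere in the protocol. The comparator also receives a ketone ester, and eligibility is not confined to amenorrhoea.

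Items 2 and 5 do keep women who do not cycle in view, but for regularity. The background section itself says that menses are not proof of ovulation, so these items do not fill the gap. Pilot status lowers the stakes without removing them, because the Impact section wants efficacy data to shape a fully powered trial.

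**Conclusion.** The point holds in conditional form. The sole between-arm analysis addressing the primary outcome has a denominator that treatment can change. Unless open intervals are scored, it omits women who are clear failures. Under assumed rates the per-cycle comparison can shrink, vanish or reverse relative to the per-woman comparison: for example +4.0 points against −7.5, or 40% versus 20% against 67% versus 80%. These figures show what is possible, not what to expect; neither size nor direction can be read from the documents. The mismatch between a woman-level outcome and a cycle-level unit follows from the protocol's own text and does not depend on the assumed rates.

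**What to change.** Make the main ovulation analysis per woman:

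- **Outcome:** at least one confirmed ovulation, yes or no, within a fixed calendar window from diet start, adjusted for baseline ovulation or cycle status because the stated outcome is a change.
- **Population:** all randomised women by assigned arm. A woman with no bleed and no detected ovulation counts as not ovulated.
- **Dropouts:** a stated rule rather than exclusion, since restricting to women observed for the whole window would again select on a post-randomisation event. One option is to count them as not ovulated, with a sensitivity analysis. Another is time to first confirmed ovulation, censored at dropout. The background cites a 24-week study in which 5 of 11 women completed (45%), so the rule could matter.
- **Per-cycle results:** keep as description, with the definition of a cycle written down.
- **Window length:** set it once the 12-week statement in the synopsis and the 8-week statement in the Diet Intervention section are reconciled.

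No new measurements are needed: the nightly sensor and daily urine tests run in calendar time whether or not a woman bleeds. The cost is protocol and analysis wording, including which signals together count as a confirmed ovulation. The downside is that one yes/no result per woman carries less detail than cycle-level data. A supporting count of ovulations per 28 days of observation recovers part of it.

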Participants will be randomized into either a ketogenic diet arm or a mixed diet with ketone ester arm. During the first 2 weeks, participants will be provided food meeting either the Ketogenic diet requirements, or mixed diet (following the USDA dietary macronutrient recommendations) at a caloric level estimated at 100% of energy requirements. The participants randomized into the Mixed diet arm will also receive a ketone ester supplement. This will be provided throughout the study. Energy requirements will be determined using a combination of information obtained from testing including habitual diet assess through an NIH sponsored food frequency questionnaire (e.g., DHQ-III which will be sent to the participants email) , body mass and composition, and formulas (e.g., Harris-Benedict) that consider sex, age, height and activity patterns.

All participants will be provided all their meals and snacks selected to meet all calorie needs via individualized pre-ordered groceries and/or prepared food for the first 2 weeks of the diet. We have established the infrastructure for conducting controlled feeding studies for other funded research including development and implementation of 7-day

rotational menus, hybrid feeding approaches (providing groceries), and use of ready-

Primary	Changes in anovulatory status in women with PCOS
Secondary	
Changes in reproductive hormones such as progesterone, estrogen, LH, FSHAnalysis of potential predictive metabolic baseline characteristicsDifferences in blood metabolites (metabolic and lipids).
Exploratory	
Examine cardiovascular function and ovarian morphology using magnetic resonance imaging (MRI).

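### The only between-arm analysis of ovulation treats cycles as independent although women are randomised, so the uncertainty of the diet effect may be understated

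*Protocol*

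**What the plan says.** The primary outcome is "Changes in anovulatory status in women with PCOS" (Outcomes). Allocation is by woman: "Participants will be randomized into either a ketogenic diet arm or a mixed diet with ketone ester arm" (Diet Intervention), with 20 women per arm (Sample Size).

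The analysis section has five items. Only item 3 addresses the effect of the diet on ovulation, through a logistic regression for "the incidence of ovulation in PCOS women, considering each cycle as an independent statistical unit", "considering potential confounders like age, BMI, and initial menstrual cycle characteristics". The rest do not compare ovulation between arms:

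- Item 1 describes cycles and ovulation status at baseline.
- Item 2 compares time to regular cycles.
- Item 4 states: "Hazard ratios and their confidence intervals will be calculated to quantify the influence of the ketogenic diet on attaining regular menstrual cycles".
- Item 5 states: "The proportion of participants achieving regular menstrual cycles in each diet group will be compared". Here the woman is the unit, but the endpoint is regularity.

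No section gives a random effect, a GEE, a cluster-robust variance or a one-result-per-woman summary for ovulation.

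**The concern.** Independence of cycles is written into the plan as a rule. It is not a detail left open for a statistical analysis plan, and a later plan that clustered on the woman would contradict the protocol.

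Ovulation is tracked daily throughout, so every cycle a woman has on study can become a row. Two cycles from one woman share her underlying tendency to ovulate and her diet arm. Counting them as two independent observations credits the arm comparison with more information than it holds.

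The regularity analyses cannot stand in for item 3, because the protocol's own background (Ketogenic Interventions in PCOS) says that having menses does not establish ovulation.

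What is at stake is precision. The stated aim is: "Our intent is to produce preliminary feasibility and efficacy data to inform the design of a future fully-powered, clinical trial". If the interval around the diet effect is too narrow, the designers of that trial will trust the estimate more than 40 women can justify.

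**Working it through.** **Plan's own figure.** The protocol gives 40 women with no alpha, power, effect size or event rate, so there is no calculation to reproduce.

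**Inputs from the protocol.** 20 women per arm; regular cycle 21–35 days (item 2); intervention 12 weeks (Study Synopsis) or 8 weeks (Diet Intervention).

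**Assumptions, none in the protocol.** Within-woman correlation ρ of 0.1–0.7; ovulation probability 0.4 per cycle; two-sided 5% test; no true diet effect; for simulated calendars, ovulatory cycles of 26–32 days and anovulatory cycles of 40–100 days.

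**Step 1: cycles per woman (m), if regular.**

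- 12 weeks: 84/35 = 2.4 to 84/21 = 4.0.
- 8 weeks: 56/35 = 1.6 to 56/21 = 2.7.

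Oligomenorrhoeic women will give fewer, so m = 3 is an upper case for them.

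**Step 2: design effect.** DE = 1 + (m − 1)ρ. The true standard error is √DE times the one reported. Actual error = 2[1 − Φ(1.96/√DE)].

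| m | DE (ρ 0.1 to 0.7) | √DE | Actual error |
|---|---|---|---|
| 1 | 1.0 | 1.0 | 5% |
| 2 | 1.10–1.70 | 1.05–1.30 | 6.2–13.3% |
| 3 | 1.20–2.40 | 1.10–1.55 | 7.4–20.6% |
| 4 | 1.30–3.10 | 1.14–1.76 | 8.6–26.6% |

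Example: m = 3 and ρ = 0.5 give DE = 1 + 2 × 0.5 = 2.0. The 40 × 3 = 120 cycles carry the information of 120/2 = 60, and the true standard error is √2.0 = 1.41 times the reported one.

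**Step 3: simulation.** Each woman has a beta-distributed ovulation probability. The table gives the true error of a nominal 5% Wald test across ρ = 0.1–0.7. It is shown unadjusted, then adjusted for three baseline covariates that explain none or half of the between-woman variance. Open means that intervals unfinished at the end of follow-up also count as rows.

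| Rows analysed | Unadjusted | Adjusted |
|---|---|---|
| Two cycles per woman | 6.5–13.8% | 5.6–13.4% |
| Three cycles per woman | 7.6–20.9% | 6.5–21.5% |
| 84 days, entry at cycle start, completed | 6.1–9.2% | 6.3–9.5% |
| 84 days, entry at cycle start, open | 7.5–16.5% | 7.3–16.9% |
| 84 days, mid-cycle entry, completed | 3.6–4.3% | 2.0–4.5% |
| 84 days, mid-cycle entry, open | 6.1–12.8% | 5.5–13.6% |
| 56 days, entry at cycle start, completed | 2.3–2.7% | 0.8–2.6% |
| 56 days, entry at cycle start, open | 6.3–9.5% | 6.4–10.1% |
| 56 days, mid-cycle entry, open | 4.2–6.9% | 3.9–7.4% |

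With 56 days, mid-cycle entry and completed cycles only, the unadjusted error is about 0 and the adjusted model converges in only 5–11% of runs.

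For 84 days with entry at cycle start, standard errors are too small by a factor of 1.08–1.21 (completed; mean 1.2 cycles per woman, 16% of women with no row) or 1.13–1.45 (open).

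Where the Wald test is not inflated, sparse counts make it conservative; the cycles are still not independent. The score test of the same unadjusted comparison rejects 6.6–7.6% (84 days, mid-cycle, completed) and 5.8–6.4% (56 days, cycle start, completed).

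**Step 4: the remedy.** The adjusted model clustered on the woman, with a Kauermann-Carroll correction and a t reference, was run at ρ = 0.1 and 0.7. It gives 2.9–5.1% for two cycles, three cycles and 84 days with entry at cycle start, and 1–2% for sparse mid-cycle completed counts. The Mancl-DeRouen correction is conservative, at 1.0–3.5%. One row per woman, unadjusted, gives 3.8–4.2%.

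**Step 5: weighting.** A woman's number of cycles depends on whether she ovulates. With completed cycles over 84 days and ρ = 0.3, shortening only the anovulatory cycles from 40–100 to 36–60 days moves the per-cycle ovulation rate from 59% to 50%, although no woman's probability per cycle has changed.

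**The case against.** The strongest reply is that the harm may be small here. Women enter with "Participants with PCOS symptoms including oligomenorrhea-anovulation or spontaneous intermenstrual periods", so many may complete one cycle or none, and with one row per woman there is nothing to cluster. The higher 84-day and 56-day figures also assume entry at the start of a cycle, which the protocol text does not require. With mid-cycle entry they fall, at 56 days close to nominal. This stands, and it is why the claim is that uncertainty may be understated.

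The 40% ovulation rate is also a choice. At 20% the unadjusted results are broadly similar. At 10%, counting non-estimable fits as non-rejections, two cycles give 1.6–4.0% and three cycles 4.5–11.7%. Sparse counts cause much of that drop, and standard errors can still be too small.

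Three further points stand in part:

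- The protocol sets no alpha and ties no decision to item 3, so the standard-error factor measures the harm better than a false-positive rate.
- The covariates help only as far as they explain differences between women; where they explain none, the adjusted error is no lower.
- Clustering corrects the variance only. It does not restore women with no row or remove the weighting effect of step 5, both of which depend on a cycle-counting rule that a statistical analysis plan may define.

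The pilot label and the acknowledged low power limit the weight of the point but do not answer it. A small sample is a reason to report uncertainty correctly.

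**Conclusion.** The concern holds and should be fixed. Item 3 states an independence assumption that conflicts with randomisation by woman, in the only analysis that compares the primary outcome between arms. The model understates the uncertainty of the diet effect whenever women give two or more cycles and ovulation is positively correlated within a woman.

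Under the assumptions listed, the shortfall in the standard error runs from a few per cent to about half with two or three cycles per woman. For an 84-day calendar with entry at cycle start it is 8–21% (completed cycles) or 13–45% (open intervals also counted). With sparse completed cycles the Wald test is not inflated. The direction does not depend on the assumed values, but the size does. The effect is mainly on precision and on what is carried into the later trial, because no decision rest on this test.

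**What to change.** Delete the clause in item 3 that declares cycles independent, and make the woman the cluster. Suggested wording:

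> Ovulation per observed cycle will be analysed by logistic regression on diet arm, age, BMI and baseline cycle characteristics, fitted by GEE with the woman as cluster, a small-sample-corrected sandwich variance and a t reference.

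The correction is needed because there are only 40 clusters. A mixed-effects logistic model is a possible alternative. It was not simulated here, and with little more than one cycle per woman its variance component would be poorly estimated.

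As an alternative estimand, use one ovulation outcome per randomised woman over a fixed window, built from the daily temperature and urine LH data already collected. This also deals with women who complete no cycle and with unequal weighting, but it answers a different question and discards repeat ovulations.

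Separately, the 8-week and 12-week statements of the intervention length must be reconciled, because they set the observation window.

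The cost is a change of wording and wider, more honest intervals; no new data are needed.

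### The ovulation regression (Statistical Plan, item 3) has an open list of baseline terms for 40 women with few ovulations; an unpenalised fit would moderately exaggerate a real diet effect

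*Protocol*

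**What the plan says.** The protocol's primary outcome is change in anovulatory status. In the section on data analysis and statistical methods, only item 3 compares ovulation between the arms; items 2, 4 and 5 concern cycle regularity. Item 3 reads "We will utilize logistic regression analysis to assess the effect of the ketogenic diet on the incidence of ovulation in PCOS women". The unit of analysis is fixed by the phrase "considering each cycle as an independent statistical unit", and the adjustment is described as "considering potential confounders like age, BMI, and initial menstrual cycle characteristics". Item 3 also promises that "This analysis will offer quantifiable insights into the probability of ovulation in the study population".

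Item 1 gives an idea of what the cycle characteristics might be: "menstrual cycle attributes such as cycle length, variability, and ovulation status for participants at baseline". It does not say that these three are the terms meant in item 3.

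The Sample Size paragraph sets a "sample size of 20 participants in each intervention", says that "for this pilot trial we plan to recruit 40 participants to investigate the effects on ovulation", and acknowledges that the small sample limits power. No ovulation rate, effect size or drop-out rate is assumed. No estimation method beyond logistic regression is named.

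**The concern.** Logistic regression by maximum likelihood is biased away from no effect when there are few events per coefficient, and the bias grows with each added term. Here the population is selected for not ovulating, the sample is 40, and the adjustment list has no upper limit. Because the arms are randomised, the baseline terms are not needed to remove systematic confounding. They can only help precision or chance imbalance, so each weakly prognostic term costs more than it returns.

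The Impact section says that the pilot's efficacy data will inform the design of a larger trial. An exaggerated OR carried into that design would make the next trial too small.

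**Working it through.** **Inputs from the protocol.** 40 women, 20 per arm; the cycle as the unit; age, BMI and baseline cycle characteristics as covariates. With one cycle term the model has 4 coefficients besides the intercept (diet, age, BMI, one cycle term). With all three attributes from item 1 it has 6.

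**Assumptions, since the protocol gives none.** Comparator ovulation p0 = 10%, 20% or 30%; true OR 3.

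**Cycles per woman.** Item 2 puts the upper limit of a regular cycle at 35 days. In 12 weeks (synopsis) 84/35 = 2.4; in the 8 weeks given under Diet Intervention 56/35 = 1.6. Women with longer cycles therefore complete at most two, or at most one. One to two or one to three records per woman covers this, with one record per woman as the lower end.

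**Events per coefficient.** p1 = OR·p0 / (1 − p0 + OR·p0). At p0 = 20%: 0.6/1.4 = 0.429. With one record per woman, events = 20 × 0.20 + 20 × 0.429 = 12.6.

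| p0 | p1 | Events, one record per woman | Per coefficient, 6 terms | Per coefficient, 4 terms |
|---|---|---|---|---|
| 10% | 25% | 7.0 | 1.2 | 1.8 |
| 20% | 42.9% | 12.6 | 2.1 | 3.1 |
| 30% | 56.3% | 17.3 | 2.9 | 4.3 |

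With 1–2 cycles (mean 1.5) the 20% row becomes 18.9 events, or 3.1 per coefficient with 6 terms. With 1–3 cycles (mean 2) it becomes 25.1, or 4.2.

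**Size of the exaggeration.** Simulation with about 400 to 1,000 trials per setting, 40 women, diet plus five covariates, true OR 3; geometric mean of the finite estimates:

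- 1–3 or 1–2 independent cycles per woman, p0 10–30%: about 3.5–4.1. With two to three cycles it can be as low as 3.4.
- One record per woman: about 3.9–4.3.
- No true effect: the estimate centres on 1, and 4–5% of tests reject (one record per woman).

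**What drives it.** One record per woman, p0 20–30%, covariates without effect of their own: maximum likelihood with five covariates 4.1–4.2; with two covariates 3.4–3.6; Firth with five covariates 3.1. Fewer terms help, and the penalty removes most of the bias even with all five.

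**Precision.** 40 women, 1–2 cycles, p0 20%, same five covariates: RMS error of log OR 0.83 (maximum likelihood) against 0.67 (Firth). (0.67/0.83)² = 0.65, so mean squared error is about 35% lower.

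**Share of simulated trials with no finite estimate (five covariates).**

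| Women analysed | Cycle as unit, p0 20–30% | Cycle as unit, p0 10% | One record per woman, p0 20% or more |
|---|---|---|---|
| 40 | 0–1% | up to about 7% | 0.3–5% |
| 32 (20% lost) | about 1–2%, at most 4% | 2–20% | 2–10% |
| 18 (55% lost) | 1–28% | 24–59% | 31–64% |

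With one record per woman, 40 women and p0 10%, the share is 21–26%.

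**If cycles within a woman are correlated** (between-woman standard deviation 1.5 on the logit scale). The OR of 3 is then conditional on the woman. The population-averaged OR is about exp(ln 3 / √(1 + 0.346 × 1.5²)) = exp(1.099/1.334) = 2.3. The cycle-level fit with 40 women averages 2.4–2.6: above 2.3 but below 3. With no true effect its nominal 5% test rejects in 8.5–14%.

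**The case against.** The strongest reply is that item 3 does not fix the model examined here. Its covariates are examples, item 1's list is also illustrative and not tied to item 3, and maximum likelihood is not mentioned. The final list and the estimator are commonly left to a statistical analysis plan, which is not at hand. This stands: six coefficients is an upper reading, and the result is conditional on a standard fit. What the protocol does fix is an adjusted logistic regression with an unbounded list, in 40 women, with cycles treated as independent.

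A second reply is that the cycle, not the woman, is the unit, so there are more rows and less bias. This also stands in part. In one setting with about 80 independent cycles the mean was 3.36; ln(3.36/3) = 0.11, and 0.11²/0.70² is about 3% of the mean squared error. Most of the error is then small-sample variance, which the protocol acknowledges. With the one or two cycles that women with long cycles can complete, the bias is larger.

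A reader might go further and infer any of the following; the documents do not support them.

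- *The analysis will overstate the diet effect.* Not with no true effect, and not against the woman-level OR if cycles are correlated.
- *Realistic drop-out will often leave no finite estimate.* The only retention figure, 5 of 11, comes from a cited 24-week single-arm study. At 20% loss and 20–30% comparator ovulation the share is a few per cent at cycle level.
- *Age and BMI must be dropped.* A Firth fit with all five terms already averages about 3.1.
- *An odds-ratio model contradicts the promise about probability.* Predicted probabilities follow directly from a logistic model.

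**Conclusion.** The point holds in a limited form. If item 3 is fitted by standard maximum likelihood with about five baseline terms, a true OR of 3 is reported on average as about 3.5–4.1 at cycle level and 3.9–4.3 with one record per woman, and with more error than a penalised fit of the same model. These figures assume 40 analysed women, 10–30% comparator ovulation and independent cycles; a shorter covariate list gives less bias. Failure to obtain a finite estimate is a secondary risk, frequent only near 10% comparator ovulation or with about half the women lost.

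The independence assumption is a separate defect in the same sentence, and it is explicit in the text. Changing the estimator alone would leave it in place. The change is worth making because item 3 is the only planned between-arm analysis of the primary outcome and a better method costs almost nothing.

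**What to change.** Reword item 3 so that it:

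1. names a short, closed covariate list: one or two prognostic baseline variables already collected, such as one baseline cycle measure and BMI, described as prognostic covariates and not as confounders;
2. fits the model by Firth-penalised logistic regression with profile-likelihood confidence intervals;
3. removes the statement that cycles are independent, and either uses one ovulation result per woman or a penalised fit that accounts for clustering within the woman;
4. reports the standardised probability of ovulation in each arm and the risk difference with a 95% confidence interval, beside the OR.

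If one result per woman is chosen, the penalty matters more, because there are only about 7 to 17 events in the settings above. Firth's penalty also pulls predicted probabilities slightly towards one half (for 4 of 20 with no covariates, 4.5/21 = 21.4% instead of 20%), so an intercept-corrected version should be used for step 4.

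Cost: a few sentences and a standard software option; no new data or visits. The downsides are fewer covariates in the model, slight shrinkage of the estimate and, with one result per woman, some loss of cycle-level detail, which can still be described. The fix does not remove the low power that the protocol already acknowledges.
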